3.4 Secondary Outcomes

- **HIV incidence:**

Number of new HIV infections per 100 person-years, based on seroconversion during follow-up, using data from the Ministry of Public Health national HIV database.

- **Incidence of Chlamydia and Gonorrhea infections:**

Number of new chlamydia and gonorrhea infections identified at each follow-up round, based on self-collected urine and anal specimens.

- **Sexual risk behavior:**

Proportion of participants reporting condomless anal intercourse with male partners in the past 6 months, measured via self-reported survey data.

- **Retention in HIV care:**

Proportion of HIV-positive participants who remain engaged in HIV care at months 6, 12, 18, and 24, based on data from the Ministry of Public Health national database.

- **Undetectable viral load:**

Proportion of HIV-positive participants with a viral load of <200 copies/mL at each follow-up round, as reported in the Ministry of Public Health national database.

- **Current PrEP use:**

Proportion of HIV-negative participants who report currently using PrEP at each follow-up round, based on self-reported data.

4. Analysis Populations

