1.1 Overview of the Problem

Thailand is currently experiencing an alarming HIV epidemic among young men who have sex with men (YMSM), particularly those aged 15–29. In Bangkok, HIV prevalence among YMSM aged 18–24 is as high as 31%. The HIV incidence rate in this group is approximately 12%, which is the highest level documented in Asia.^{1,2} These rates far exceed those in high-risk populations in the United States, where even the most at-risk group, Black MSM, has an incidence rate of around 4%.³ Contributing risk factors among Thai YMSM include being paid for sex, having sex at saunas, and living away from family. The HIV prevalence in northeastern provinces like Ubon Ratchathani and Mahasarakham ranges between 10%–25%, which is over ten times higher than the national average. If no effective prevention strategies are implemented, other regions in Thailand may follow the same trajectory as Bangkok.

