1.2 Supporting Evidence

Despite the high risk, very few YMSM are accessing HIV testing or care. According to a joint study conducted by the US CDC and the Thai Ministry of Public Health, only 50.3% of MSM in Thailand had ever been tested for HIV. Of those, merely 24.9% returned for their test results.⁴ As a result, only 12.5% actually knew their HIV status.⁵ Our previous research found that 73.3% of YMSM aged 15–19 and 45% of those aged 20–24 had never tested for HIV.⁶ This indicates that current HIV prevention efforts are failing to reach adolescents and young adults, especially in terms of HIV testing and linkage to care. Furthermore, many healthcare providers, including HIV test counselors, lack adequate knowledge of the Continuum of Prevention and Care (CPC), especially regarding the importance of achieving viral suppression, and often perpetuate stigma and discrimination against YMSM. These systemic issues further hinder engagement in HIV prevention and treatment services.

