2.2 Eligibility criteria

Inclusion Criteria:

- Aged between 15 and 29 years
- Currently residing, studying, or working in either Warin Chamrap District or Mueang District of Ubon Ratchathani Province (intervention site), or in Kantharawichai District or Mueang District of Mahasarakham Province (control site)
- Intend to remain in the study area for at least the next three years
- Assigned male at birth
- Self-identify as gay, men who have sex with men (MSM), bisexual, or *toot* (a locally understood term)
- Have engaged in anal sex (insertive or receptive) with a male partner within the past 12 months
- Willing and able to provide informed consent to participate in the study

Exclusion Criteria:

- Aged ≤ 14 years or ≥ 30 years
- Not currently residing, studying, or working in one of the designated study areas
- Planning to move out of the study area within the next three years
- Assigned female at birth
- Self-identify as a woman, transgender woman, or transfeminine individual
- Unwilling to participate in follow-up activities associated with the study

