1.2 Background and Significance of the Study

This study aims to evaluate the efficacy of the BAAN HUG-M intervention in:

- Reducing sexual risk behaviors
- Increasing the frequency of HIV testing (at least biannually)
- Promoting prompt and sustained engagement in HIV care

The study is conducted through a longitudinal cohort of young men who have sex with men (YMSM) (“YMSM Cohort”, $N = 600$) residing in Ubon Ratchathani (intervention site) and Mahasarakham (control site). Given the disproportionate burden of HIV among YMSM in Thailand, and the structural and behavioral barriers to care, this study addresses a critical public health challenge with implications for national HIV policy and intervention programming.¹⁻³

2. Study Design Overview

This will be a prospective, longitudinal cohort study involving 600 young men who have sex with men (YMSM) aged 15–29 years, with equal allocation to two study sites:

- Intervention city: Ubon Ratchathani ($n = 300$)
- Control city: Mahasarakham ($n = 300$)

Participants will be followed for 24 months, with data collection scheduled at five time points: baseline, 6 months, 12 months, 18 months, and 24 months.

Data Collection and Sources

Data will be collected through online self-administered questionnaires hosted on the Qualtrics platform and completed using tablets or smartphones. To ensure anonymity while enabling longitudinal data linkage, no personal identifiers will be recorded. Instead, participants will enter a Unique Identification Code (UIC) at each round of data collection.

Retention and Follow-up

To promote high retention throughout the study period, the research team will implement continuous engagement strategies via digital platforms and peer-led community outreach. These efforts are expected to result in follow-up retention rates of greater than 60% at each follow-up time point.

3. Study Objectives and Endpoints

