3.1 Primary Objective

To evaluate the effectiveness of the BAAN HUG-M intervention in increasing access to and engagement with the intervention activities, and in promoting HIV testing uptake among young men who have sex with men (YMSM) who have never previously been tested for HIV.

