3.2 Secondary Objectives

- To evaluate the effect of the intervention on reducing HIV incidence.
- To evaluate the effect of the intervention on reducing the incidence of chlamydia trachomatis and gonorrhea infections.
- To evaluate the effect of the intervention on reducing sexual risk behaviors (e.g., condomless anal intercourse).
- To evaluate linkage to and retention in HIV care among HIV-positive participants, including the proportion with undetectable viral load.
- To evaluate the uptake of pre-exposure prophylaxis (PrEP) among HIV-negative participants.

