4.1 Intention-to-Treat (ITT) Population

The ITT population will include all participants who completed the baseline assessment and were assigned to either the intervention or control site, regardless of their level of

participation in the intervention activities thereafter. This population will serve as the primary analytic population for evaluating the effectiveness of the intervention, reflecting real-world implementation outcomes.

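### HIV incidence is counted only from national-database tests, with no risk-set or person-time rule, so the rate ratio can reflect unequal detection between the two cities

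*Combined protocol and SAP*

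**What the plan says.** SAP 3.2 sets a secondary objective: "To evaluate the effect of the intervention on reducing HIV incidence". SAP 3.4 measures it as "Number of new HIV infections per 100 person-years, based on seroconversion during follow-up, using data from the Ministry of Public Health national HIV database". No other source is named for this outcome.

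Protocol sections 2 and 2.1.2 describe urine samples and rectal swabs, tested for chlamydia and gonorrhea. No HIV test by the study is described at baseline or follow-up. The HIV data to be extracted from the database include the date of the latest test and HIV status.

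The primary objective in SAP 3.1 includes "promoting HIV testing uptake among young men who have sex with men (YMSM) who have never previously been tested for HIV". SAP 1.2 adds testing at least twice a year as an aim. SAP 3.3 takes the primary outcome, testing uptake, from the same database.

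On the analysis, protocol 2.4.2 and SAP 6.2 say that person-time will be calculated and rate ratios reported with 95% confidence intervals. They give no rule for entry, exit, untested time or the dating of infection. On the population, SAP 4.1 states: "The ITT population will include all participants who completed the baseline assessment and were assigned to either the intervention or control site". The eligibility list in protocol 2.2 has no HIV-status criterion. SAP 5.1 (missing data) concerns drop-out and missed visits, and SAP 7.2 lists only changes of model.

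**The concern.** An infection enters this outcome only if the man is tested somewhere that reports to the database. If the intervention changes testing, it changes the chance that an infection is seen, apart from any effect on infection itself. A rate ratio that divides detected infections by all follow-up time mixes the two.

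Infections already present at baseline add to the problem. The protocol's background gives a prevalence of 10% to 25% in provinces such as these, and reports that "73.3% of YMSM aged 15–19 and 45% of those aged 20–24 had never tested for HIV". Some men may therefore enter with undiagnosed infection, and without a documented negative a first positive in such a man cannot be told from a new infection.

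The stake is the reading of the HIV incidence objective. A true reduction may be attenuated, hidden or, with a large enough gap in detection, reversed; a gap the other way would exaggerate it. Because the person-time rule is open, it could also be chosen after the data are seen, among rules that give materially different answers.

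**Working it through.** The plan gives no expected HIV event count, no incidence for the study cities and no testing rate by city, so there is no figure of its own to reproduce.

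**Inputs from the documents:** 300 men per city and 24 months of follow-up, hence 300 × 2 = 600 person-years per city if all time is counted.

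**Assumptions:** control incidence L = 0.05 per year; true ratio 0.70, so L = 0.035 in the intervention city; all men negative at baseline; constant testing rate, unrelated to risk; p = proportion tested at least once in 24 months.

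**Formulas**
- Testing rate: m = −ln(1 − p)/2. For p = 40%, m = 0.255.
- Expected detected infections per city: 300 × ∫₀² L e^(−Lt) (1 − e^(−m(2−t))) dt.
- If a negative and a later positive are both needed in follow-up, the integrand is also multiplied by (1 − e^(−mt)).
- Both cities have 600 person-years, so the observed ratio is the ratio of expected counts.

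The share of new infections detected by month 24 is about 22% (p = 40%), 25% (45%), 28% (50%) and 35% (60%).

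| Tested, control/intervention | Detected, control vs intervention | Observed ratio (true 0.70) | Ratio if negative and later positive both needed in follow-up |
|---|---|---|---|
| 40/45 | 6.29 vs 5.07 | 0.81 | 0.90/0.97 = 0.93 |
| 40/50 | 6.29 vs 5.71 | 0.91 | 1.16/0.97 = 1.20 |
| 40/60 | 6.29 vs 7.07 | 1.12 | 1.83/0.97 = 1.89 |
| 60/50 | 10.00 vs 5.71 | 0.57 | not used |

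In the third column the ratio crosses 1 at about 54% tested in the intervention city when control is at 40%. Varying control incidence from 2 to 10 per 100 person-years moves the first three ratios by about 0.01. Ending person-time at the first recorded positive changes the ratios by at most 0.04.

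**Precision at 40/60:** the standard error of the log ratio is √(1/6.29 + 1/7.07) = 0.548, so the 95% CI is 1.12 × e^(±1.96 × 0.548), about 0.38 to 3.29. In the last column fewer than two events are expected per city.

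**Undiagnosed infection at baseline, counted as new.** With a share u undiagnosed in both cities, the expected count is (1 − u) times the count above plus 300 × u × p. For u = 5% to 10%, a true 0.70 appears as 0.85 to 0.91 at 40/40, 1.08 to 1.14 at 40/50 (12.0 vs 12.9 and 17.7 vs 20.1 cases) and 1.31 to 1.38 at 40/60.

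**What drives the direction.** It is the share of infections detected, not the share of men tested. Suppose that in control only, half the men have 1.5 times and half 0.5 times the average risk, with testing following the same multipliers and p fixed. At 40/45, control then detects 27% of infections against 25% in the intervention city, and a true 0.70 appears as 0.65.

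**Second model.** A simulation used 6-month rounds, a 3-fold risk difference between two halves of the men, twice the testing probability per round in the intervention city, incidence of 2, 4 or 12 per 100 person-years and u of 0, 5 or 10%. With a true ratio of 1.00 and testing unrelated to risk, counting untested time gives 1.44 to 1.76; equal testing gives 0.99 to 1.01. Counting only time between documented tests gives 0.96 to 1.03. If testing is tied to risk in one city only (incidence 4, u = 5%), the between-test ratio runs from 0.73 to 1.54.

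**The case against.** The strongest reply is that seroconversion already implies a prior negative test, so first positives without one would not be counted. That is the natural reading, and it would remove the baseline-infection problem. It does not settle which negative counts, how old it may be, or whether men without one leave the denominator. If they stay in and both tests must fall in follow-up, the distortion is larger (last column of the table). Protocol 2.1.2 names the latest test date, which for a diagnosed man may be the positive test itself. Its list is introduced as non-exhaustive, so it does not show that full histories are unavailable.

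Three further points stand. The testing rates are assumed, so no size can be claimed for this trial. Few events are expected, and the ratio would be imprecise under any rule. Restricting to tested intervals is no complete cure, since it selects on testing after baseline and can err either way.

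A reader might infer that the ratio goes up whenever testing rises more in the intervention city. The documents give no starting level of testing in either city, so this does not follow: if control testing is higher to begin with, the intervention city can gain more and still end lower. At 60/50 a true 1.00 appears as 8.07/10.00 = 0.81.

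**Conclusion.** The concern holds. Detection of the HIV outcome depends on the behavior that the intervention aims to change, and the plan contains neither a risk-set and person-time rule nor an analysis that addresses unequal detection. Confidence in that is high.

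Confidence in direction and size is lower. With untested time counted, the bias is upward if the intervention city has the larger detected share of infections and downward if it has the smaller. Baseline infections counted as new, with a similar undiagnosed share in both cities, move a true reduction further towards or past 1. If that share differs the effect can go the other way: with 10% undiagnosed in control and 5% in the intervention city, a true 1.00 appears as 0.86 at 40/50.

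A reader might also infer that a successful intervention would necessarily have its effect hidden or reversed. The documents do not support that. At 40/45 and 40/50, with no undiagnosed infection, the effect is only attenuated, and reversal needs a gap of testing that the plan neither states nor predicts. This point concerns one secondary outcome and leaves the primary outcome untouched. It should be fixed before the analysis.

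**What to change.** In SAP 3.4, 6.2 and 7.2:

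1. Report the all-participant database count as *new HIV diagnoses*, show testing frequency by city beside it, and do not interpret its ratio as an effect on incidence.
2. Reserve *incidence* for a supportive estimate in participants with a documented negative test and a later test.
   - Start person-time at the later of baseline and the first documented negative, so that no pre-baseline time counts. End it at the last negative or the estimated seroconversion date.
   - State in advance how seroconversion is dated, for example at the midpoint between last negative and first positive. Where the last negative precedes baseline, use an interval-censored method or report those cases separately.
   - Report first positives without a prior negative separately. Give event numbers and the confidence interval, and state that the estimate conditions on testing and may be biased either way.
3. Request all test dates and results from the database. If they are unavailable, report only new HIV diagnoses.
4. Add a sensitivity analysis that varies, separately by city, the share of new infections detected and the share undiagnosed at baseline (for example 0, 5 and 10%), and report the values at which the conclusion changes.

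The cost is SAP wording, a little more analysis and a fuller data extraction, with no new visits or specimens. The incidence estimate will rest on few events with a wide confidence interval, and the sensitivity analysis depends on assumed shares.

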1.4 Objective

To evaluate the efficacy of Baan HUG-M in decreasing sexual risk behavior; increasing HIV testing to at least biannually; and increasing prompt, sustained engagement in care among YMSM living with HIV by using a longitudinal cohort of YMSM in Ubon Ratchathani and Mahasarakham

2. Study design and methods of data collection

This study aims to evaluate the effectiveness of the Baan HUG-M intervention, a community-based strategy designed to promote HIV prevention and facilitate access to care among young men who have sex with men (YMSM) aged 15 to 29 years. A longitudinal cohort design is employed across two geographic locations: Ubon Ratchathani (intervention site) and Mahasarakham (control site), with a total sample size of 600 participants (300 per site). The follow-up period spans 24 months, with data collection occurring at five time points: baseline and months 6, 12, 18, and 24.

Data collection comprises self-administered surveys completed via the Qualtrics platform⁷ and self-collected biological specimens, including urine samples and rectal swabs, for chlamydia and gonorrhea testing. All specimens will be transported to and analyzed at the Office of Disease Prevention and Control 10 (ODPC 10), located in Ubon Ratchathani Province. Additionally, study data will be linked to the national HIV database maintained by the Ministry of Public Health. To protect participant confidentiality, no personally identifiable information is collected within the survey. Instead, a Unique Identification Code (UIC) is assigned to each participant to enable secure and systematic linkage of data across multiple sources.

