2.1.2 Data Collection

Data will be collected at five time points: baseline, and months 6, 12, 18, and 24 of follow-up. At each round, participants will complete self-administered surveys using tablets or smartphones via the Qualtrics platform. A Unique Identification Code (UIC) will be used to longitudinally link participant data across time points. The UIC will consist of the first letter of the province name, followed by an underscore, the first two letters of the participant's last name, and the date of birth in the DDMMYYYY format (e.g., P_AB01012025). To minimize entry errors, local research staff will select the UIC from a predefined list using a forced-choice format.

At each follow-up round, participants will self-collect biological specimens, including urine samples and rectal swabs, for chlamydia and gonorrhea testing. All specimens will be transported under temperature-controlled conditions to the Office of Disease Prevention and Control 10 (ODPC 10) in Ubon Ratchathani for laboratory analysis. Prior to specimen collection, participants will watch a standardized instructional video to ensure correct self-collection procedures.

HIV-related clinical data including the date of the most recent HIV test, HIV status, initiation of antiretroviral therapy (ART), treatment continuity, and viral load results will be extracted from the national HIV database maintained by the Ministry of Public Health using the participant's national identification number. Access to this database will be restricted to the principal investigator and the study statistician to ensure data confidentiality. All data will be stored in encrypted and password-protected formats on secure institutional servers.

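### Viral suppression (and, less clearly, retention) is scored at study rounds among men known to be HIV-positive, so an intervention that raises testing can bias the between-city comparison in either direction

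*Combined protocol and SAP*

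**What the plan says.** SAP 3.4 has two outcomes on HIV care. Retention is the "Proportion of HIV-positive participants who remain engaged in HIV care at months 6, 12, 18, and 24". Viral suppression is the "Proportion of HIV-positive participants with a viral load of <200 copies/mL at each follow-up round, as reported in the Ministry of Public Health national database". Both are timed by study visit, and both are restricted to HIV-positive participants.

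HIV status and care data come from the national database. Protocol 2.1.2 lists the items extracted as including "the date of the most recent HIV test, HIV status, initiation of antiretroviral therapy (ART), treatment continuity, and viral load results". The study's own specimens are tested only for chlamydia and gonorrhoea.

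The aims are wider than a status at each visit. Protocol 1.4 speaks of "increasing prompt, sustained engagement in care among YMSM living with HIV", and SAP 3.2 sets out "To evaluate linkage to and retention in HIV care among HIV-positive participants, including the proportion with undetectable viral load". The primary objective in SAP 3.1 includes "promoting HIV testing uptake among young men who have sex with men (YMSM) who have never previously been tested for HIV".

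The model in SAP 6.2 is a GEE with arm, time and their interaction. SAP 4.1 defines one analysis population, everyone with a baseline assessment, and no set based on HIV status or date of diagnosis. SAP 5.1 allows multiple imputation or maximum likelihood under missing at random, with pattern-mixture sensitivity analyses. The one sensitivity analysis listed in SAP 7.2 varies the model form.

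**The concern.** Suppression develops on a clock that starts at diagnosis and treatment; the outcome is read on a clock that starts at enrolment. At month 12, a man in care for years and a man diagnosed at month 11 are in the same denominator, although the second has had little time to reach a result below 200 copies/mL and may have none on record.

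That would matter less if the mix of recent and long-standing diagnoses were the same in both cities. A testing intervention is designed to change that mix. An undiagnosed man is not in the denominator; once he tests positive he enters it, with little time since diagnosis. The intervention can thus alter who is scored and how long they have been diagnosed, and the alteration differs by round. It goes directly into the arm-by-time term from which SAP 6.2 estimates the effect. A between-city difference could then be read as better or worse care when care is the same.

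Promptness of engagement, which Protocol 1.4 names, can only be timed from diagnosis, so scoring by study month does not measure it. SAP 3.2 names linkage, but SAP 3.4 defines no linkage outcome.

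**Working it through.** The documents give no expected rate, effect size or power for the care outcomes, so there is no figure to reproduce. The check is a reading of the definitions (above) plus two illustrations with identical care in both cities.

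**One round.** Assumed: 30 men per city diagnosed before enrolment, 90% suppressed; 20 against 5 new diagnoses in the six months before the round, 40% of them suppressed in both cities.

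- More testing: (30 × 0.9 + 20 × 0.4) / 50 = 35/50 = 70%.
- Less testing: (30 × 0.9 + 5 × 0.4) / 35 = 29/35 = 82.9%.
- Difference: -12.9 points, although 6 more men are suppressed.

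With 10 against 5 new diagnoses: 31/40 = 77.5% against 82.9%. With 20 against 10, and 60% of new diagnoses suppressed: 39/50 = 78% against 33/40 = 82.5%.

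**Four rounds.** Let H be HIV-positive men per city, K = kH those known at baseline, q the probability that an undiagnosed man is diagnosed in six months, and L the months after diagnosis before a result below 200 is possible, with 90% suppressed from then on. No new infections or dropout.

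- Diagnosed by month t: D(t) = (H - K) × [1 - (1 - q)^(t/6)].
- Outcome as defined: P(t) = 0.9 × [K + D(t - L)] / [K + D(t)].

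Protocol 1.1 gives prevalence of 10% to 25%, so H = 30 to 75 per 300. Protocol 1.2 gives 12.5% of MSM knowing their status, used here as a low value for k. The other inputs are assumptions. Example with H = 30, k = 50%, q = 40% against 10%, L = 6:

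| Month | More testing | Less testing | Difference (points) | Suppressed per 300 enrolled |
|---|---|---|---|---|
| 6 | 13.5/21.0 = 64.3% | 13.5/16.5 = 81.8% | -17.5 | 4.5% v 4.5% |
| 12 | 18.9/24.6 = 76.8% | 14.85/17.85 = 83.2% | -6.4 | 6.3% v 5.0% |
| 18 | 22.14/26.76 = 82.7% | 16.07/19.07 = 84.3% | -1.5 | 7.4% v 5.4% |
| 24 | 24.08/28.06 = 85.8% | 17.16/20.16 = 85.1% | +0.7 | 8.0% v 5.7% |

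Over k = 12.5% or 50%, q = 40% v 10% or 50% v 20%, and L = 3 or 6, the difference ranges are:

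- month 6: -29.3 to -4.2 points
- month 12: -6.4 to +3.4
- month 18: -1.5 to +7.2
- month 24: +0.6 to +7.4

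Prevalence changes the counts but not these percentages. Scored only from L months after diagnosis, both cities give 90% at every round, a difference of 0, which is the truth under identical care.

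**Absent results.** Suppose, in the month 6 example, that the recently diagnosed men (6.0 and 1.5) have no viral load on record. Scored as not suppressed, the cities read 64.3% and 81.8%. Left out as missing, both read 13.5/15 = 90%. The unstated rule alone moves the gap from -17.5 points to 0.

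**The case against.** Percent suppressed among known positives is a coherent cross-sectional figure, and SAP 4.1 aims at real-world outcomes. These are secondary outcomes, and testing uptake, the primary, is reported beside them. In the one-round case the 95% margin on the difference is about ±18 points (1.96 × √(0.70 × 0.30/50 + 0.829 × 0.171/35)), so a 12.9-point gap would not be distinguishable from zero. All of this stands. It supports keeping the figure as a description; it does not make the between-city difference an effect on care.

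A reader might infer four stronger things that the documents do not support:

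- That a recently diagnosed man counts as a failure. That is the literal result of being in the denominator and not the numerator, but no rule says so. SAP 5.1 could treat an absent viral load as missing, although imputing it from men long in care would itself be doubtful.
- That the bias runs against the intervention. It does at month 6 in the illustration, but it fades and then reverses, because the men diagnosed earlier have had longer to reach suppression.
- That new diagnoses are added in the intervention city only. Men in the control city also test; what matters is the difference in pace.
- That retention is distorted to the same degree. The SAP does not define remaining engaged, and a man diagnosed at month 11 and linked promptly might count as engaged at month 12. No size can be shown.

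**Conclusion.** The concern holds in this form. For viral suppression, and less clearly for retention, the denominator and its time since diagnosis can be changed by the intervention, and no section of the plan corrects for it. With identical care, the between-city difference and the arm-by-time term can be biased in either direction, with the sign depending on the round. The sizes shown rest on assumed baseline knowledge of status, diagnosis rates and lag to suppression; they show what the definition permits and do not estimate this trial's bias. Separately, the plan does not say whether a man with no viral load on record is unsuppressed or missing. The outcomes are secondary, but they are the only two in SAP 3.4 that address engagement in care, and the correction is cheap.

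**What to change.** In SAP 3.4:

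1. Make the between-city comparison of suppression the number with a result below 200 copies/mL among all enrolled participants in each city at each round. Include baseline, so that it is read as a change from baseline. This denominator is fixed at enrolment and testing cannot alter it.
2. For men diagnosed during follow-up, report suppression and retention at fixed intervals after diagnosis (for example 6 and 12 months) among those with that much follow-up. Label this descriptive, because being diagnosed is itself affected by the intervention.
3. Report men already positive at enrolment at months 6 to 24 as a supporting analysis. It should not be the sole comparison: if only 12.5% know their status, it holds about 4 to 9 men per city (300 × 10% × 12.5% = 3.75; 300 × 25% × 12.5% = 9.4), and it leaves out the never-tested men whom SAP 3.1 targets.
4. Keep percent suppressed among known positives as a descriptive cross-sectional figure. State how an absent viral load is scored, and define linkage and remaining engaged.
5. Name the diagnosis date and viral-load dates in the Protocol 2.1.2 extract. That list is not exhaustive, so they may be available, but the documents do not confirm it.

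The cost is SAP wording and, if available, extra dated fields from a database already being accessed. The drawbacks are small groups with wide intervals, late diagnoses that do not reach the later interval, and an all-enrolled figure that combines the effects of testing and care.
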